The current project will test the efficacy of an Implicit Theory of Personality (ITP) intervention, which has provided excellent results in US both for depression and externalizing problems such as aggressive behavior. The project includes two studies, one focused on depression and another one focused on aggressive behavior. In addition, we will evaluate at which developmental stage the intervention is more effective. Finally, we will examine the moderation role of sex. The project includes biological data in a subsample of participants. Therefore, the project will contribute from a biopsychosocial and interdisciplinary perspective to the development of universal preventive interventions for depression and aggressive behavior, two important psychological problems in modern societies.

Preventive approaches to depression and aggressive behavior

Several depression prevention programs have been developed, such as the Coping with Stress program (Clarke et al., 1995), the Blues Program (Stice, Burton, Bearman, & Rohde, 2007), the UK Resilience Program (Challen, Machin, & Gillham, 2014), and the Penn Resiliency Program (Cardemil, Reivich, Beevers, Seligman, & James, 2006). Most prevention programs have targeted factors that have been found to increase risk for future onset of depression or increases in depressive symptoms, such as negative cognitions, social skill deficits, and ruminative style. The results from meta-analytic reviews of the effects of depression prevention programs for youth indicate that although results are good for indicated and selective preventive interventions, the average effects of universal preventive interventions on depressive symptoms from pretest to posttest are small (Mychailyszyn, Brodman, Read, &

Kendall, 2012; Stice, Shaw, Bohon, Marti, & Rohde, 2009). Interestingly, Stice et al. (2009) found that relatively shorter prevention programs produced significantly larger intervention effects than did longer prevention programs. Therefore, the authors concluded that long programs may not appeal to youth, which causes greater attrition and attenuated intervention effects. Thus, they recommended the use of brief interventions for future studies.

Regarding aggressive behavior several multicomponent interventions with elements directed towards children and adolescents as well as towards their parents and teachers have been developed and have been found to be effective. Some noteworthy examples are the Coping Power (Lochman & Wells, 2002), the Fast Track (Conduct Problems Prevention Research Group, 2002), the Montreal Preventive Treatment Program (Tremblay, Masse, Pagani, & Vitaro, 1996) and the Incredible Years programs (Webster-Stratton, Reid, & Stoolmiller, 2008). Although these programs have demonstrated to be useful, they are expensive in terms of duration and involvement of various actors (parents, schools, students).

Need of universal brief interventions

In recent years numerous short-term psychosocial interventions have been developed in educational settings with striking effects on several outcomes such as student performance, social integration, and psychological wellbeing (see for a revision Yeager & Walton, 2011). Rigorous field experiments have shown that the effects of such interventions persist for months or even years later. For example, Blackwell, Trzesniewski, and Dweck (2007) got to substantially improve school skills through an intervention based on implicit theories of intelligence, which consisted of showing that intelligence is modifiable and grows when the individual works with effort in challenging tasks. In another intervention, Walton and Cohen (2007, 2011) found that leading students to attribute worries about social integration to the difficulty of the transition to college rather than to students' personal or racial identity can strengthen ethnic minority students' sense of social belonging in school and increase motivation and performance. Furthermore, students who received the intervention reported being happier and healthier in a 3 years posttreatment follow up.

These psychosocial interventions in school can be brief yet impactful because they rely on a rich tradition of research on persuasion and attitude change to powerfully convey psychological ideas (Yeager & Walton, 2011). The crucial elements that contribute to the success of these interventions are the focus on students' experience in school from the students' perspective and the use of impactful delivery mechanisms (Yeager & Walton, 2011). Some of these mechanisms are the following: a) Active role of students, which facilitates deeper message processing; b) Interventions are stealthy. For example, interventions are not presented to the students with the intent to improve performance or other attributes. Thus, students do not feel they are being manipulated so that resistance to intervention is reduced. This approach

contributes also to avoid the stigmatization of students. Moreover, the brevity of the interventions also helps to be stealthy. c) Psychosocial interventions have effects over long periods due to recursive processes affecting effects that accumulate over time. Students usually forget the message and the details of the intervention, but this recursive nature triggers other social, psychological and cognitive mechanisms over time.

Implicit theory of personality (ITP) interventions for emotional and behavioral problems

Recently, Yeager and colleagues have extended this type of brief interventions to prevent emotional and behavioral problems such as depression and aggressive behavior in adolescents. Their approach is based on implicit theories of personality, which refer to the beliefs that people endorse about the malleability of people's socially-relevant traits. An entity theory of personality involves the belief that personal characteristics are fixed and cannot be changed whereas an incremental theory of personality involves the belief that people can change. Past research has found that when adolescents or adults believe that people's traits are fixed and unchangeable, they are more likely to attribute a negative social event (e.g., peer victimization) to their negative traits. They also will tend to infer that the same negative events and other adversities will repeat in the future. Therefore, an entity theory of personality predicts greater shame and negative emotions in adolescents when they cope with stressors such as peer conflicts (Yeager, Trzesniewski, Tirri, Nokelainen, & Dweck, 2011). By the contrary, if adolescents believe that traits can be changed, then their own traits can be improved so that it is unlikely that they become recipients of the same negative events in the future. Furthermore, other people' traits, including those of bullies, can also change. Therefore, the beliefs involved in an incremental theory of personality can be helpful not only for victims but also for perpetrators of bullying. As additional support to this, Rudolph (2010) found that holding an entity theory of peer relationships was associated with a greater tendency to evaluate oneself negatively in the face of peer disapproval and display depressive and aggressive symptoms when victimized.

Yeager and colleagues have developed brief interventions aimed to change entity theories by means of efficient and persuasive intervention tactics that are based on the above mentioned mechanisms. For instance, in one of these interventions, a six-session high school classroom intervention teaching an incremental theory reduced aggressive behavior by 40%, improved depressive symptoms two weeks post-intervention, and increased school attendance (Yeager, Trzesniewski, & Dweck, 2013). Later, they tested the effects of a shorter intervention consisting of only one session. This single session touch an incremental theory via computers. In this session 9th grade students read a scientific article about the possibility of personality change, then they read quotes from older students transmitting the same message. Finally, the students

wrote a brief essay where they defended the same idea with the aim of transmitting the message to other students in the future. Despite the brevity of this intervention, the results obtained by means of a double-blind randomized experiment showed that it reduced levels of self-reported clinically relevant depression (Miu & Yeager, 2014) and stress levels (Yeager et al., 2014).

II. AIMS AND HYPOTHESES

Aim 1: To replicate the effect of an intervention based on Implicit Theories of Personality (ITP) on depressive symptoms (Study 1) and aggressive behavior (Study 2) in a large sample of Spanish adolescents. Grounded on the previous findings obtained in US samples, we will test the efficacy of the ITP intervention by comparing changes in depressive symptoms and aggressive behavior from pretreatment to follow up between the group receiving the ITP intervention and a control group that will receive a control educational condition.

Hypothesis: Those adolescents receiving the ITP intervention will show fewer symptoms of depression and lower frequency of aggressive behavior than the control group after the intervention and at six-month and one-year follow-up.

Aim 2: To test whether the intervention changes biological and cognitive variables. From a biopsychosocial perspective, several mechanisms can explain the effect of the ITP intervention on psychological problems (depression and aggressive behavior). These mechanisms include changes in cognitive vulnerabilities and changes in the biological responses to the environmental stressors. If participants develop beliefs that personality traits are malleable, this should influence many maladaptive cognitive schemas. In fact, a feature of most maladaptive cognitive schemas is their absolute and stable nature (e.g., "I am a bad person", "The others will always reject me", "People hurt me on purpose", "I cannot put limits to my conduct". The intervention could also change biological indicators of stress (e.g., hormonal indicators). Therefore, in this project we will evaluate whether the ITP intervention affects cognitive vulnerabilities and biological indicators (cortisol, testosterone and DHEA in saliva).

Hypothesis: the association between the intervention and changes in psychological problems will be associated with changes in cognitive and hormonal variables. Some studies have explored whether the effects of interventions on depressive symptoms are mediated by changes in cognitive vulnerabilities with mixed results (Mychailyszyn et al., 2012). Thus, this project aims to contribute to clarifying mediational cognitive mechanisms.

Aim 3: To identify whether development and sex moderates the effects of the intervention. Regarding the developmental stage at which the preventive intervention is more effective, though studies are inconclusive, in general there is some consensus that cognitive vulnerabilities tend to consolidate in adolescence. Also in the case of

depression prevalence rates increase dramatically during adolescence. This supports the tentative hypothesis that the preventive intervention may be more effective if implemented early (i.e., before depression rates increase and cognitive vulnerabilities are consolidated).

As girls display higher rates of depression and boys higher rates of some modalities of aggressive behavior, sex could moderate the effects of the ITP intervention on psychological problems. For instance, we hypothesize that the ITP intervention will lead to a higher reduction of depressive symptoms in girls.

Aim 4: To test whether temperament moderates the effect of the intervention. We hypothesize that the intervention will be more effective in adolescents high in neuroticism.

III. METHODS

This project will use a randomized controlled trial study design with pretest, posttest, six-month follow-up, and one-year follow-up. Group 1 (experimental group) will receive the ITP intervention and Group 2 (control group) will receive an educational intervention.

Study design and participants

We will conduct a double-blind randomized controlled trial (RCT) with two parallel groups in a large sample of volunteer adolescents (approximately n=900), from several high school centers (ages from 12 to 18 years). The schools will be randomly selected from the Basque Country. Participants will be randomly assigned to the experimental vs control groups. Group assignation will be done at the individual level within each classroom. Participants were randomized in a 1:1 ratio blocked by gender to one of two groups (experimental versus control condition). They were assigned to their allocated group in class by the researchers.

Measures

Depressive symptoms and aggressive behavior will be assessed by means of self-reports through the Center for Epidemiologic Studies Depression scale (CES-D; Radloff, 1977), the revised version of the Peer Experiences Questionnaire (RPEQ; Prinstein, Boergers, & Vernberg, 2001), the Cyber Bullying Questionnaire (CBQ; Calvete, Orue, Estévez, Villardón, & Padilla, 2010; Gámez-Guadix, Villa-George, & Calvete, 2014).

Measures of cortisol, DHEA and testosterone in saliva: A subset of the participants (around 50%) will provide saliva samples to be assayed for neuroendocrine levels to measure cortisol, DHEA and testosterone. Saliva samples will be collected at baseline (one week before the intervention), post-intervention (one week after the intervention) and at the two follow-ups (six-months and one-year follow-up). Data collection will occur in school and the time of assessments will remain

the same for each individual to minimize the effects of diurnal rhythms and reduce error variance. The adolescents will complete an intake survey (e.g., eating, drinking, exercise, and medication) that can potentially affect hormonal reactivity. The adolescents will then be directed to transfer saliva from their mouths to a tube. The sample tubes will be carefully labelled. As soon as the session ends, saliva samples will be sent to the assay laboratory.

Cognitive vulnerabilities: Two important cognitive vulnerabilities will be assessed: dysfunctional cognitive schemas and beliefs about implicit theories of personality. We will measure cognitive schemas that are relevant for depression (i.e., defectiveness, emotional privation) in the study about depression. We will use the Spanish version of the Young Schema Questionnaire (YSQ; Young, 2006). In addition, we will measure implicit theories of personality through the Implicit Theories of Personality questionnaire (Yeager et al., 2014).

Temperament traits: Temperament will be assessed by the revised version of the Early Adolescent Temperament Questionnaire (EATQ-R; Ellis & Rothbart, 2001) and the Big Five Questionnaire for children (BFQ-C; Barbaranelli, Caprara, Rabasca, & Pastorelli, 2003) for adolescents at the beginning of the study.

Parent reports: Parents will be invited to participate by responding measures about their children temperament by means of the revised version of the Early Adolescent Temperament Questionnaire (EATQ-R; Ellis & Rothbart, 2001) and the Big Five Questionnaire for children (BFQ-C; Barbaranelli et al., 2003) for parents and depressive symptoms through the CBCL 6/18 (Achenbach, 1991; Achenbach & Edelbrock, 1983). These data will be used in analyses in case that the response rate is enough.

Preventive Intervention

The **ITP intervention** lasts one session (of approximately one hour) and has three main parts: (1) scientific information; (2) normative stories from upperclassmen; and (3) self-persuasive writing exercise. In the first part, students read a scientific article that provides evidence that individuals have the potential to change. Participants read about actual neurological and behavioral studies showing that behaviors are controlled by “thoughts and feelings in brains,” and that pathways in the brain have the potential to be changed under the right circumstances. In the second part, participants read several normative quotes purportedly written by upperclassmen that previously read the same article and endorsed its conclusions. These quotes are obtained from previous interventions and edited by the team. These testimonials are provided to bring credibility to the incremental theory. Finally, in the last part, participants will be asked to write their own version of such a narrative to share with future students. This activity has been shown to facilitate the internalization of the intervention message,

building on a long line of research on cognitive dissonance (Walton & Cohen, 2011). For a more complete description of the ITP intervention see Yeager et al. (2013). The intervention will be adapted to the developmental characteristics of the participants.

The **educational intervention** involves scientific information about the human brain. It was designed to be parallel to the experimental intervention and, hence, it has also three main parts. First, participants are asked to read scientific information about the different areas of the brain and their specialties. Second, participants read several testimonials written by upperclassmen about their transition to high school and how their brains help them to adapt to the new space and all the physical differences of the building and the classes. Finally, participants are asked to write a letter to another student explaining the main things he or she has learned about the brain and thinks are important for adapting to the new physical environment in high school. Hence it will control for the possibility that simple optimism about the potential for growth might account for our results. This is a conservative control group. An entity theory control group would be unethical in a longitudinal field experiment because it could teach the belief that personality cannot be changed, which has been associated to negative consequences.

Procedure

Parental informed consent forms will be sent to parents and adolescents. Those who accept to participate in the study will complete report measures at four waves: (1) one-week before intervention; (2) one-week after intervention; (3) six-months follow-up; and (3) one-year follow-up. Saliva samples will be collected at the same time points. Parents' participants will complete report measures at three waves: (1) one-week before intervention; (2) six-months follow-up; and (3) one-year follow-up. Intervention will be applied one week after the first survey. All the measures will be anonymous and participants will be asked to provide certain data (her/his birth date, first initial of mother's name, and first initial of father's name) to match their questionnaires, saliva samples and intervention tasks over time. Both interventions and assessment measures will be administered by research assistants during normal class time and last around 50 minutes.

Ethical considerations

This study aims to develop and implement interventions that will be beneficial for the participating adolescents and other people in the future, by helping to increase their psychological wellbeing. Through randomization, the principle of justice will be respected, allowing all participants to have similar opportunities to receive the intervention. Gender will be considered and similar number of male and female participants will be included in the studies.

The risks are minimal and limited to answering psychological tests on stressors, psychological symptoms and cognitive styles. Previous experience with the same

questionnaires indicates that the risk is minimal. Adolescents can also decide to end their participation at any moment. Researchers collecting data will be trained to attend to any difficulty that could emerge while participants are responding to questionnaires. The researchers will give an alternative task (e.g., educational readings) to those participants who decide to end their participation.

Informed consent forms will be sent to parents or legal guardians to complete. Adolescents will also receive written information. The active consent of parents or legal guardians and of adolescents will be necessary for participation in the project. We will incentive adolescents for bringing parent forms, even when decision is negative.

Parents will be invited to complete measures of children's temperament and send their completed questionnaires in a stamped envelope that will be provided without any identifying information. Adolescents will complete the measures in the classroom. Saliva samples and their analysis will be processed according to existing regulations in a professional lab.

After completing measures, adolescents will be provided with information on services for adolescents (e.g., phone number of attention to adolescents). From an ethical perspective, the most important care aspect is the protection of information. We will follow the Directive 95/46/EC of the European Parliament, *Ley Orgánica 15/99 de 13 de diciembre de Protección de datos de Carácter Personal*, and of the Council of 24 October 1995 on the protection of individuals with regard to the processing of personal data and the free movement of such data. No identification data, such as names or surnames, will be used; instead, we will use a numeric code to match measures across times and sources (parents, and adolescents). Thus, each adolescent, and only he/she, will know his/her code. We will also follow the procedure for data protection that the University of Deusto has registered in the National Data Protection Agency. The project has been approved by the Ethics in Research committee of University of Deusto.

IV. STATISTICAL ANALYSES PLAN

Descriptive statistics of sociodemographic and study variables will be provided and several statistical strategies will be used to test the hypotheses. These will include mixed analyses of variance (ANOVA), multilevel analyses, regression analyses, among others. We will use IBM SPSS, MPLUS, LISREL, and HLM software for analyses.

References

Achenbach, T. M. (1991). Child Behavior Checklist/4-18 and 1991 profile. *Burlington, Vermont, USA: University of Vermont, Department of Psychiatry*.

Achenbach, T. M., & Edelbrock, C. S. (1983). Manual for the Child Behavior Checklist/4-18 and revised child behavior profile. *Burlington, Vermont, USA: University of Vermont, Department of Psychiatry*.

Blackwell, L. S., Trzesniewski, K. H., & Dweck, C. S. (2007). Implicit theories of intelligence predict achievement across an adolescent transition: A longitudinal study and an intervention. *Child Development*, 78(1), 246-263. doi:10.1111/j.1467-8624.2007.00995.x

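### Aim 1 is framed as a comparison of changes and the SAP does not commit to baseline adjustment; at an assumed correlation of 0.4 to 0.7, adjusting matches a 900-pupil change-score analysis with 135 to 270 fewer pupils

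*Combined protocol and SAP*

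**What the plan says.** In II. Aims and Hypotheses, Aim 1 is to be tested by "comparing changes in depressive symptoms and aggressive behavior from pretreatment to follow up between the group receiving the ITP intervention" and the control group. The hypothesis directly below is in terms of levels: the intervention arm is expected to show "fewer symptoms of depression and lower frequency of aggressive behavior than the control group" after the intervention and at both later follow-ups.

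Section IV (Statistical Analyses Plan) is one short paragraph. On methods it says: "These will include mixed analyses of variance (ANOVA), multilevel analyses, regression analyses, among others". It does not link a method to an aim, name a covariate or say how the pretest score enters the model.

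Three design features matter here:

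- Allocation is individual, within classrooms. Under Study design and participants: "Participants were randomized in a 1:1 ratio blocked by gender to one of two groups".
- The same section describes the sample as "in a large sample of volunteer adolescents (approximately n=900" and gives no calculation behind that number.
- Under Procedure, "Those who accept to participate in the study will complete report measures at four waves", the first of them one week before the intervention. The baseline score will therefore be available.

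The introduction adds: "The project includes two studies, one focused on depression and another one focused on aggressive behavior". The documents do not say whether each study uses all 900 pupils.

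**The concern.** The only contrast the documents name for Aim 1 is a comparison of changes. The first method listed in the SAP, mixed ANOVA, delivers exactly that contrast for any single pre-to-follow-up pair through its group-by-time term. After randomisation the arms have the same expected baseline. Subtracting the whole baseline score, rather than the part that predicts follow-up, then adds noise without removing bias.

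Precision matters in this trial. The protocol's own review of earlier work says that "the average effects of universal preventive interventions on depressive symptoms from pretest to posttest are small", and the intervention is one session of about an hour. Leaving the estimator open also means that change, level and adjusted results could all be produced, with nothing on record to say which one answers Aim 1.

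**Working it through.** **Inputs.** From the documents: about 900 pupils, 1:1 individual allocation, one baseline and three follow-ups. Assumed, because the documents give none: correlation ρ between baseline and follow-up, standardised effect d (in follow-up SD units), ratio of SDs, number analysed, two-sided 5% level, no missing data. The figure of 900 cannot be reproduced, because no inputs to it are stated.

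**Variances.** Let s0 and s1 be the baseline and follow-up SDs.

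- Change score: s0² + s1² − 2ρ·s0·s1
- Adjusted for baseline: s1²(1 − ρ²)
- Difference: s0² − 2ρ·s0·s1 + ρ²·s1² = (s0 − ρ·s1)², which is never negative

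With equal SDs set to 1, the two variances are v = 2(1 − ρ) and v = 1 − ρ². Their ratio (adjusted to change) is (1 + ρ)/2, so the saving is n(1 − ρ)/2.

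**Single follow-up wave, n = 900, d = 0.20.** SE = √(4v/n) and power = Φ(d/SE − 1.96). At ρ = 0.4:

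- Change: SE = √(4 × 1.20/900) = 0.0730, and Φ(2.74 − 1.96) = 0.78.
- Adjusted: SE = √(4 × 0.84/900) = 0.0611, and Φ(3.27 − 1.96) = 0.91.

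| ρ | v, change | v, adjusted | Matching n | Fewer pupils | Power, change | Power, adjusted |
|---|---|---|---|---|---|---|
| 0.4 | 1.20 | 0.84 | 630 | 270 | 0.78 | 0.91 |
| 0.5 | 1.00 | 0.75 | 675 | 225 | 0.85 | 0.93 |
| 0.6 | 0.80 | 0.64 | 720 | 180 | 0.92 | 0.96 |
| 0.7 | 0.60 | 0.51 | 765 | 135 | 0.97 | 0.99 |

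Outside that range the saving is 315 pupils at ρ = 0.3 and 90 at ρ = 0.8. With 900 kept, the difference detectable with 80% power falls from 0.205 to 0.171 SD at ρ = 0.4, and from 0.145 to 0.133 SD at ρ = 0.7.

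**Four-wave mixed ANOVA.** With all four waves the overall group-by-time interaction is a 3-df test and no longer equals a single change contrast. Assume exchangeable correlation and the same d at every follow-up. The non-centrality is then (n/4)d² × 0.75/(1 − ρ) for the interaction, and (n/4)d² × 3/[(1 − ρ)(1 + 3ρ)] for the joint test of the three follow-ups adjusted for baseline. At ρ = 0.4 and d = 0.20 these are 9 × 0.75/0.6 = 11.25 and 9 × 3/(0.6 × 2.2) = 20.45. Power for interaction against adjusted test:

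- d = 0.20: 0.81 against 0.98 at ρ = 0.4; 0.99 against more than 0.99 at ρ = 0.7
- d = 0.15: 0.54 against 0.82 at ρ = 0.4; 0.86 against 0.94 at ρ = 0.7

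**Sensitivity of the single-wave result.**

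- Baseline SD 10% below the follow-up SD: 65 to 206 fewer pupils (ρ 0.7 to 0.4). Baseline SD 10% above: 215 to 332.
- Correlation falling over time, for example 0.7 at one week, 0.6 at six months, 0.5 at one year: 135, 180 and 225 fewer.
- Loss to follow-up of 10%: 122 to 243 fewer analysed pupils. Loss of 30%: 95 to 189.
- 450 pupils per study: about 68 to 135 fewer, with power at d = 0.20 of 0.49 against 0.64 (ρ = 0.4) and 0.78 against 0.84 (ρ = 0.7).
- d = 0.25 with 900 pupils: the change score already has power of about 0.93 at ρ = 0.4, so little is gained.

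**Simulation check.** With 900 pupils, d = 0.20 and 4,000 simulated trials per setting, single-wave power for change and adjusted analyses was 0.776 and 0.900 at ρ = 0.4, and 0.974 and 0.986 at ρ = 0.7. With no effect and ρ = 0.5 (10,000 trials), the two single-wave and two 3-df tests rejected in 4.9% to 5.1% of trials.

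**The case against.** The strongest reply is that the plan has not chosen the weaker analysis. Aim 1 states a purpose, and comparing changes is compatible with adjustment: regressing change on arm and baseline gives the same treatment coefficient as regressing follow-up on arm and baseline. The SAP lists regression and multilevel methods, either of which could carry the baseline score. The loss arises only if the investigators later take the unadjusted option. This stands as a limit: the plan leaves the choice open and does not decide against adjustment. It does not remove the point, because nothing in the plan commits to adjustment either.

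Every magnitude is assumed, and the range of 135 to 270 also needs equal SDs and 900 pupils analysed. That is correct, and modest departures widen it to 65 to 332. Nobody proposes to recruit fewer pupils, so detectable difference or power is the more practical scale. The 3-df figures bear on the mixed ANOVA and not on wave-specific estimates, for which the single-wave table applies. The formulas also do not carry over if the frequency of aggressive behaviour is analysed with a count model, so they fit the depression score better.

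Finally, baseline adjustment is only one of several things the short SAP leaves unspecified. That is true, but this item has a specific answer that uses data already planned.

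**Conclusion.** The concern holds, as a matter of precision and not of validity. The plan names a comparison of changes for Aim 1, states its hypothesis in levels and does not commit to baseline adjustment. In this design adjustment is at least as precise in large samples whatever the correlation or SDs.

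The gain is material if the correlation is towards 0.4, the effect is 0.20 or smaller, or each study has about half of the 900 pupils. It is small at correlation 0.7 with all 900, where a true effect of 0.20 is missed 3% of the time against 1%; at correlation 0.4 the figures are 22% against 9%. These results rest on the assumed correlation, effect and SDs, and on complete data. The change is worth making but is not critical to the trial.

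**What to change.** State in section IV that the Aim 1 treatment effect, for each outcome at each follow-up in the hypothesis (post-intervention, six months, one year), is estimated in one named way. Two are suitable:

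- a model for the follow-up score with the baseline score of the same outcome as a covariate; or
- a multilevel model over all waves with a common baseline mean across arms and treatment-by-wave terms.

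Include all randomised pupils in their assigned arm and all observed waves. Keep change scores and the group-by-time mixed ANOVA as supportive results. Reword Aim 1 so that it and its hypothesis describe the same contrast. If a count model is chosen for aggressive behaviour, say so and state how baseline enters it.

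The cost is wording. No extra pupils, visits or measurements are needed, and the listed software (SPSS, Mplus, HLM) fits models of this type.
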